Key notes regarding study setting and design: Four community substance abuse treatment agencies have partnered with the research team for this study. These four agencies have 1-9 sites each that are scattered around Western Washington for a total 15 sites. Each site varies from 1-3 Intensive Outpatient Program (IOP) groups which run simultaneously. Each IOP has approximately 24-36 sessions of 2-3 hours each (72 hours total). Once they complete all sessions, the IOP restarts. New IOP clients enter the program at any time and stay till they have attended all 24 or 36 sessions. Thus, each Step in this Stepped Wedge design will be an entirely new set of clients.

Only one IOP for each site will be selected to be the focus of this study (Selected IOP). All client participants will be recruited and consented by research staff and the interventions (TAU vs. PARS) will be in the Selected IOP.

Within each Step, data collection will be as follows. Two weeks prior to the week Standard/PARS session is to be conducted in the selected IOP, research staff will connect with counselors at that site to (a) set up a plan for client recruitment and (b) have counselors complete online assessments themselves. One week prior to the Standard/PARS session, the research staff will come to the program 1-3x to recruit participants with the goal of recruiting all willing participants enrolled in that Selected IOP. Baseline assessments completed at recruitment. Follow-up assessments online or by phone two weeks, then one, three, and six months after recruitment.

Administrative Supplement: We will conduct a sub-study to culturally tailor PARS for use in Alaska Native and American Indian (ANAI) communities. This will be conducted in three ANAI communities with whom [name] and/or [name] are currently collaborating.

1.7 Intent. Check all the descriptors that apply to your activity. You must place an "X" in at least one box.

This question is essential for ensuring that your application is correctly reviewed. Please read each option carefully.

Descriptor
 1. Class project or other activity whose purpose is to provide an educational experience for the researcher (for example, to learn about the process or methods of doing research).
 2. Part of an institution, organization, or program's own internal operational monitoring.
 3. Improve the quality of service provided by a specific institution, organization, or program.

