2 PARTICIPANTS

2.1 Participants. Describe the general characteristics of the subject populations or groups, including age range, gender, health status, and any other relevant characteristics.

Client participants (N=900) will be adults with a substance use disorder (SUD) that resulted in their admission to the selected IOP (Selected IOP). All clients enrolled in the Selected IOP will be recruited to participate.

Counselor participants (N=~50, maximum 200) are chemical dependency providers and/or clinicians working at the study sites. To determine effects of PARS implementation beyond the Selected IOP all counselors who work at all the sites will be recruited to participate including any counselors newly hired across the course of the study.

Administrative Supplement: [REDACTED]

2.2 Inclusion and exclusion criteria. Describe the specific criteria you will use to decide who will be included in your study from among interested or potential subjects. Define any technical terms in lay language.

Assumed by virtue of placement that they would be eligible (refer to section 4.1)

Client Participant Inclusion Criteria

1. Enrolled client in one of the community treatment settings
2. Over 18 years of age (no maximum age)
3. Ability to understand written and spoken English

Client Participant Exclusion Criteria

1. Any clinical medical/psychiatric condition, severity of that condition, or life situation that in the opinion of the counselors or Drs. [name] or [name] would compromise safe and voluntary study participation (e.g., psychosis, custody conflict). This is expected to be a rare circumstance and will be known prior to the recruitment session. If a counselor does not want someone involved, they will not be. If counselor is unsure, [name] or [name] will facilitate decision with counselor ahead of time to assist in the decision.

Counselor Participants – Inclusion Criteria:

1. Hired as regular staff counselor at one of the partner agencies
2. “Engagement staff”: anyone who has a clinical treatment relationship with clients (CDPs, counselors, etc.).
3. Ability to understand written and spoken English

Counselor Participants – Exclusion Criteria:

1. Determined by agency administrator as not appropriate to participate (do not have specific expectation this will occur but want to provide agencies with possibility of excluding counselor at their discretion)

Stakeholder Participants – Inclusion Criteria:

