5 PROCEDURES

5.1 Study procedures. Using lay language, provide a complete description of the study procedures, including the sequence, intervention or manipulation (if any), time required, and setting/location. If it is available and you think it would be helpful to the IRB: Upload a study flow sheet or table to the **Supporting Documents** SmartForm in **Zipline**.

For studies comparing standards of care: It is important to accurately identify the research procedures. See UW IRB [POLICY: Risks of Harm from Standard Care](#) and the draft guidance from the federal Office of Human Research Protections, ["Guidance on Disclosing Reasonably Foreseeable Risks in Research Evaluating Standards of Care"](#), October 20, 2014.

Study Interventions

In this study, we are using a Stepped wedge design that randomizes at the site level. That means that all clients will receive whichever intervention their site is providing at the time they enroll. This will be Treatment as Usual (TAU) until the Stepped wedge design randomization selects that site to implement PARS at which point all clients will receive PARS till the end of the study. This will be true for all clients and counselors whether or not they choose to participate in the study. Thus, the study is restricting the choice of interventions for study participants and non-participants.

This is described in the consent form for participants. However, because of the study design, non-subjects will also experience randomization and exposure to the intervention. We request a waiver of consent for this.

Clarification of IOP Treatment in which both study interventions are embedded

Intensive Outpatient Program (IOP) guidelines in Washington State are based on State requirements. Within these guidelines, agencies typically offer IOP consisting of three-hour groups, three times a week, over eight weeks, for a total of 24 groups (72 hours total). Some programs meet less often for a longer time window up to 12 weeks. The 24-36 session series runs and then starts over continuously. Clients can enter the IOP at any time in the 24 session series and stay until they have attended all 24-36 sessions. Thus, within 24-36 sessions, all IOP clients will have completed (or dropped) from the program and a new group of IOP participants will be in the program. In our Stepped wedge design, each step is 4 months, which means that when we return to the site at each step, we will be recruiting from a different pool of clients.

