All IOP counselors will be trained in the Step where they are randomized to implement PARS. In this way, the study sites are “engaged” in the research as counselors on site will provide the study interventions. The agencies will be deferring human subjects review to the UW and have completed an Institutional Agreement for IRB Review (IAIR) with each site.

[name], who developed PARS, will provide all the training. To maximize the value to our community partners and assure a counselor trained in PARS is available on the day the PARS module is scheduled, all consenting counselors will be offered the opportunity to participate in the training so that someone can substitute if the designated PARS counselor is unavailable.

PARS counselor adherence will be evaluated at the first PARS administration by having an adherence coder sit in on the PARS session. Observation is the method requested by the agency treatment partners as least disruptive and most acceptable to clients. As adherence coders will have participant contact and be hearing the treatment session, they will complete any training on specific agency procedures regarding treatment observers with regard to client PHI so the adherence coders meet all agency standards. No client PHI will be collected as part of adherence coding – the focus is on the counselor’s level of adherence to PARS and not client identity nor comments.

Both Conditions:

Any additional treatments outside of the IOP program (e.g., mental health-oriented counseling, pharmacotherapy) will be available during all phases of the Stepped design. Washington State mandates self-help group attendance in addition to attendance of group and individual IOP sessions; this will also remain consistent throughout each site’s participation (regardless of when PARS is implemented at each site).

Client Participant Assessment Procedures:

Reminder – clinics are randomized at the clinic level. Clients and counselors have no choice in if they receive the intervention. This randomization effects clients and counselors regardless of whether they are study participants or not. As noted above, participants are informed about this in the consent form and we request waiver of consent for the non-participants.

Baseline Assessment

Will always occur one week prior to session intervention.

Will be conducted by in-person group administration. Assessments will be completed on paper or tablet computers. Expected to take 15-30 minutes.

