This study will use a stepped wedge design as shown in Figure 1. This design is recommended for studies in which it is beneficial to randomize at the site rather than individual level.³⁵⁻³⁷ Such is the case in this study, as randomization at the individual level would not be feasible with our community partners, who are enrolling clients and placing them in groups based on many complex reasons including client schedules, IOP group schedules and openings, and a myriad of agency guidelines and regulations. Such a study would require conducting PARS and usual care in a research clinic setting—which is the opposite of our goal. PARS was developed in community settings and its effectiveness in those settings is key. Once it was determined that randomization would be at the site level, both clustered randomized and stepped wedge designs were considered.^{35,37-44} While both have benefits, the stepped wedge has the advantage of measuring dose-response (delay) effects. Furthermore, its primary disadvantage (that more assessment points were required)^{35,40,42} was not determined to be a problem for the research team or community partners, as participants would complete the same assessments regardless of stepped wedge or cluster randomization.

In the proposed study, there will be six steps. Steps will be 6 months each to assure sufficient time for all data collection to occur given that some IOP programs are as long as 12 weeks and sites will vary as to which session PARS replaces in their IOP curricula. In each of the six steps of the study, baseline assessments will be conducted the week before that selected session at that site. For instance, Site A might replace session 8 with PARS but Site B might replace session 14, so baseline assessments will be conducted in week 7 at Site A and week 13 at Site B. (Data collection methods for baseline assessments described in Procedures below.) This will assure that the follow-up assessments reflect the period after PARS is administered while allowing the natural variation in IOP curriculum that is inevitable with 15 community partner sites.

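### Clients in their last week at baseline are counted as PARS although no PARS session falls between their baseline and follow-up, and nothing in the plan screens for or flags them

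*Protocol*

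**What the plan says.** **Admission and stay.** Protocol 5.1 says of the programme: "The 24-36 session series runs and then starts over continuously". It adds: "Clients can enter the IOP at any time in the 24 session series and stay until they have attended all 24-36 sessions". The typical format is "three-hour groups, three times a week, over eight weeks, for a total of 24 groups", and "Some programs meet less often for a longer time window up to 12 weeks".

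**The study session.** Each site fixes one session in its series as the TAU session, and PARS later replaces it (Protocol 5.1; SAP C3). Once a site starts PARS it continues through Step 6 (SAP C3, Stepped Wedge Design).

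**Baseline.** Protocol 5.1, Baseline Assessment: "Will always occur one week prior to session intervention". SAP C3 says of this timing: "This will assure that the follow-up assessments reflect the period after PARS is administered".

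**Who is recruited.** Protocol 2.1: "All clients enrolled in the Selected IOP will be recruited to participate". The design notes in Protocol 1.6 put it as "with the goal of recruiting all willing participants enrolled in that Selected IOP". The criteria in Protocol 2.2 and SAP C4 cover enrolment, age, English and safety. None concerns earlier attendance at the designated session or the number of sessions left.

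**Analysis.** SAP C.7 analyses all participants by intention to treat and tests the Treatment by Time interactions, that is, change from baseline. The mediators are changes from baseline to post-intervention. Medical records are to show how many sessions were attended and whether the programme was completed (Protocol 5.2). No use of them to identify attendance at the study session is stated.

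**The concern.** The design treats baseline as a measurement before the session and follow-up as one after it. For a client who leaves within a week of baseline, the coming session is never reached, and the designated session that the client did attend lies a full cycle back.

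What that earlier session was depends on the step:

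- **Later PARS steps (30 of 45 PARS site-steps).** It was PARS, about 7 weeks before baseline in an 8-week cycle or 11 weeks in a 12-week cycle. Baseline is already post-PARS.
- **A site's first PARS step (15 of 45).** If the recruited session is the first PARS delivery, it was the TAU session, and the client never receives PARS. For these clients the SAP's assurance about follow-up fails.

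Either way the client is coded PARS and supplies little or no PARS-related change. At stake is dilution of the Treatment by Time test for knowledge, attitudes and help-seeking, and of the mediators in Aim 3. The SAP's allowance for lost information covers under-recruitment and attrition, not this.

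**Working it through.** **1. Share in the last week at baseline.** Let C be the cycle length in weeks: 8 (typical) or 12 (longest), from Protocol 5.1. Assume steady entry, full attendance and no drop-out, so each client stays C weeks. The designated session was last given C − 1 weeks before baseline. Clients with tenure above C − 1 weeks have had it and leave before the next one:

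- share = 1/C = 1/12 = 8.3% to 1/8 = 12.5%
- of 450 PARS clients (45 site-steps × 10): 37.5 to 56.25, about 38 to 56.

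**2. Sensitivity to the unstated inputs.**

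- Drop-out at a constant rate with completion probability q: share = (q^((C−1)/C) − q)/(1 − q).
- Attendance a, with stay lengthened to C/a: share that already attended the session = a × [1 − a(C − 1)/C].

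| Assumption | 8-week cycle | 12-week cycle |
|---|---|---|
| Full attendance, no drop-out | 12.5% | 8.3% |
| Completion 80% / 70% / 50% | 11.3 / 10.6 / 9.1% | 7.5 / 7.0 / 5.9% |
| Attendance 90% / 80% / 70% | 19 / 24 / 27% | 16 / 21 / 25% |

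The last row is a wider group. Of those clients, the fraction still on the roll a week later is 1 − 1/(C/a − (C − 1)). At 80% attendance this is 1 − 1/(10 − 7) = 67% for 8 weeks and 1 − 1/(15 − 11) = 75% for 12 weeks. At 90% it is about half (47% and 57%), and at 70% it is 77% and 84%.

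**3. The plan's power figure.** SAP C.7 states 89% power at N = 900 and 80% at N = 675 for 15.6% vs 28.1% at month 1. It gives no alpha, sidedness or intraclass correlation (ICC). I used the closed-form stepped-wedge variance (random site effect, fixed step effects; 15 sites, 6 steps), two-sided 0.05.

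- Individual variance: (0.156 × 0.844 + 0.281 × 0.719)/2 = 0.1669; per site-step of 10, s² = 0.01669.
- Assumed ICC 0.005: between-site variance τ² = 0.1669 × 0.005/0.995 = 0.000838.
- Design sums: U = 45 PARS site-steps; W = 495 (squared step totals); V = 165 (squared site totals).
- Variance = 15 s²(s² + 6τ²) / [(15U − W)s² + (U² + 90U − 6W − 15V)τ²] = 0.005435 / (180 × 0.01669 + 630 × 0.000838) = 0.00154; SE = 0.0392.
- Effect/SE = 0.125/0.0392 = 3.19, so power is 89.0%. With 7.5 per site-step it is 79.7%.

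Both stated figures are reproduced, but only because the ICC was chosen to do so. ICC 0 gives 91.8%/82.7%, 0.01 gives 86.8%/77.3% and 0.05 gives 79.1%/68.5%.

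**4. Illustrative dilution at ICC 0.005.**

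- *No effect in any last-week PARS client.* 12.5 × (1 − 1/12) = 11.5 points and 12.5 × (1 − 1/8) = 10.9 points. Power is 83% to 80% at N = 900, and 73% to 69% at N = 675.
- *Earlier PARS effects last, so only the first-step third is diluted.* 12.5 × (1 − 1/36) = 12.2 points and 12.5 × (1 − 1/24) = 12.0 points. Power is 87% to 86% at N = 900.
- *Last-week clients left out and not replaced.* 9.17 to 8.75 per site-step at the full 12.5 points. Power is 86.5% to 85.0%.

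**The case against.** The strongest reply is that the SAP powers a month-1 comparison of rates between arms, not change from baseline. A later-step client who had PARS in the previous cycle may still show its effect at month 1 and so belongs in the PARS rate. That stands: the 80% to 83% figure is one extreme for that comparison, and 86% to 87% is equally consistent with the documents. It does not rescue the Treatment by Time test. If the earlier gain persists, baseline is already raised; if it fades, nothing renews it before follow-up. The SAP gives no power for that test.

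The trial is also pragmatic and analysed by intention to treat, so clients who never reach the session resemble absentees. Keeping them in that set is not an error. The gap is that a condition knowable before baseline is neither screened, recorded nor allowed for.

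A reader might infer four stronger things that the documents do not support:

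- **That a fifth or more of clients show no change because sessions are missed.** At 80% attendance two-thirds to three-quarters of those already exposed are still on the roll for the coming session. They are contaminated at baseline, not simply without change.
- **That the SAP's statement that each client experiences PARS or TAU only once is contradicted.** A fully attending last-week client has had the session exactly once, before baseline.
- **That the Aim 4 dose trend is flattened.** That model adjusts for baseline outcome, and last-week clients are unexposed in a site's first PARS step but pre-exposed in later ones. The direction is not established.
- **That every client is enrolled.** The aim is to recruit all who are willing.

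**Conclusion.** The concern holds as a modest dilution of uncertain size. The mechanism follows from the plan's own schedule, and no criterion or analysis step deals with it. The share is derived, not stated: 8.3% to 12.5% under steady entry, full attendance and no drop-out, and about 6% to 11% with the drop-out rates tried. Missed sessions bring the share already exposed at baseline to about 16% to 27%, a different and partly overlapping group. The power figures are illustrations that rest on an assumed ICC of 0.005 and a two-sided 0.05 test. They span about 80% to 87% against the stated 89%, depending on how long an earlier PARS effect lasts. The change is worth making because it is cheap and restores the before-and-after meaning of the primary test; the trial is not invalid without it.

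**What to change.** Add one criterion to Protocol 2.2 and SAP C4, assessed before baseline and applied identically in TAU and PARS steps: the client has not already attended the site's designated TAU/PARS session (or PARS earlier), and has enough sessions left to be enrolled on the day of the coming designated session. Because it uses only pre-baseline information and is the same in both conditions, it introduces no selection after baseline. Counselors already judge eligibility (SAP C5).

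If enrolment is complete, record prior attendance at the designated session from the medical record or counselor clarification (Protocol 5.2). This works only if attendance is available session by session, since the Protocol mentions only the number attended and completion. Report the primary model in the set meeting the criterion in both conditions, alongside the all-participants analysis.

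**Cost.** SAP C2 expects 12 to 15 registered clients per group. Losing 12.5% leaves about 10.5 to 13, against 10 planned. Where attendance is poor, a loss of 20% to 24% leaves about 9 to 12, so some site-steps could fall short. If excluded clients are not replaced, power at N = 900 is about 85% to 86.5%: better than keeping them if they show no effect, but no better if earlier PARS effects last. In that second case the gain is a cleaner change-from-baseline estimate rather than power.

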3 INTERNATIONAL RESEARCH SETTING

Answer the questions in this section **ONLY** if your research will occur at sites outside of the United States

3.1 Reason for sites. Describe the reason(s) why you selected the sites where you will conduct the research.

N/A

3.2 Local context. Culturally-appropriate procedures and an understanding of local context are an important part of protecting subjects. Describe any site-specific cultural issues, customs, beliefs, or values that may affect your research or how it is conducted.

Examples: It would be culturally inappropriate in some international settings for a woman to be directly contacted by a male researcher; instead, the researcher may need to ask a male family member for permission before the woman can be approached. It may be appropriate to obtain permission from community leaders prior to obtaining consent from individual members of a group.

*This federal site maintains an international list of human research standards and requirements:
<http://www.hhs.gov/ohrp/international/index.html>*

N/A

3.3 Site-specific laws. Describe any local laws that may affect your research (especially the research design and consent procedures). The most common examples are laws about:

- **Specimens** – for example, some countries will not allow biospecimens to be taken out of the country.
- **Age of consent** – laws about when an individual is considered old enough to be able to provide consent vary across states, and across countries.
- **Legally authorized representative** – laws about who can serve as a legally authorized representative (and who has priority when more than one person is available) vary across states and countries.
- **Use of healthcare records** – many states (including Washington State) have laws that are similar to the federal HIPAA law but that have additional requirements.

N/A

3.4 Site-specific administrative or ethical requirements. Describe local administrative or ethical requirements that affect your research.

Example: A school district may require you to obtain permission from the head district office as well as school principals before approaching teachers or students; a factory in China may allow you to interview factory workers but not allow you to pay them.

N/A

4 RECRUITING and SCREENING PARTICIPANTS

4.1 Recruiting and Screening. Describe how you will identify, recruit, and screen subjects. Include information about: how, when, where, and in what setting. Identify who (by position or role, not name) will approach and recruit subjects, and who will screen them for eligibility.

Client Participant Recruitment:

A week ahead, counselors will inform clients from each selected IOP that research staff will be coming by providing them the PARS client recruitment flyer (attached). Using the same flyer a week later, all clients will be reminded about the study and told to stay at the end of a group if they would like to hear more about it.

Using the recruitment flyer for talking points, the research staff will come at the end of group to explain what the study is and recruit participants.

(If a client participant does not meet study criteria, the IOP counselor will call that client aside as the IOP group ends to explain this to them privately and the client will not stay to hear about the study or participate.)

Counselor Participant Recruitment:

The agency leadership will inform counselors from each site that research staff will be coming by providing them the PARS counselor recruitment flyer (attached).

Using the recruitment flyer for talking points, the research staff will come to explain what the study is and recruit counselor participants.

All counselors (defined as staff with a treatment relationship with clients) will be invited to participate at the beginning of the study. At each subsequent Step, if new counselors have started they will be recruited at that time and will complete the remainder of the study.

(If a counselor participant does not meet study criteria, the agency staff will call that counselor aside to explain this to them privately and the counselor will not stay to hear about the study or participate.)

Stakeholder Recruitment for the Administrative Supplement:

A large rectangular area of the page is completely redacted with a solid gray color, obscuring several lines of text that were likely intended to be filled in or detailed.

4.2 Recruitment materials.

a. What materials (if any) will you use to recruit and screen subjects?

Examples: talking points for phone or in-person conversations; video or audio presentations; websites; social media messages; written materials such as letters, flyers for posting, brochures, or printed advertisements; questionnaires filled out by potential subjects.

As noted in 4.1 above, there will be two recruitment flyers – one for client participants and one for counselor participants. Both are attached.

We would like to request flexible approval of recruitment strategy and materials, specifically to create or update recruitment materials without submitting a modification to the application so long as the overall content does not go outside the scope and range of what is already approved. Any substantive change to content would be submitted as a formal modification.

b. Upload descriptions of each type of material (or the materials themselves) to the **Consent Forms and Recruitment Materials SmartForm of **Zipline**.** If you will send letters to the subjects, the letter should include a statement about how you obtained the subject's name, contact information, and any other subject-specific information (such as a health condition) that is mentioned in the letter.

HSD encourages researchers to consider uploading descriptions of most recruitment and screening materials instead of the materials themselves. The goal is to provide the researchers with the flexibility to change some information on the materials without submitting a Modification for IRB approval of the changes. Examples:

- *You could provide a list of talking points that will be used for phone or in-person conversations instead of a script.*
- *For the description of a flyer, you might include the information that it will provide the study phone number and the name of a study contact person (without providing the actual phone number or name). In doing so, you would not need to submit a Modification if/when the study phone number or contact person changes. Also, instead of listing the inclusion/exclusion criteria, you might state that the flyer will list one or a few of the major inclusion/exclusion criteria.*
- *For the description of a video or a website, you might include a description of the possible visual elements and a list of the content (e.g., study phone number; study contact person; top three inclusion/exclusion criteria; payment of \$50; study name; UW researcher).*

4.3 Relationship with participant population. Do any members of the study team have an existing relationship with the study population(s)?

Examples: a study team member may have a dual role with the study population (for example, being their clinical care provider, teacher, laboratory director or tribal leader in addition to recruiting them for his/her research).

	No
	Yes

→ If yes, describe the nature of the relationship.

[name] works extensively with substance abuse treatment sites in Western Washington and has or may consult with them on challenging cases etc. over the next five years. It is unlikely that one of the client participants will be someone he consults on, but this is not impossible. It is somewhat more likely that he would consult with a counselor participant. These consultations are at the agency's request and they are under no obligation to do so.

[name] also has a longstanding consultation relationship with the [REDACTED] Indian Tribe. [name] has been conducting another research study with both the [REDACTED] in which we have conducted a cultural tailoring process comparable to the one proposed here.

4.4 Payment to participants. Describe any payment you will provide, including:

- The total amount/value
- Whether payment will be "pro-rated" so that participants who are unable to complete the research may still receive some part of the payment

The IRB expects the consent process or study information provided to the subjects to include information about the number and amount of payments, and especially the time when subjects can expect to receive payment. One of the most frequent complaints received by HSD is from subjects who expected to receive cash or a check on the day that they completed a study and who were angry or disappointed when payment took 6-8 weeks to reach them.

Do not include a description of any expenses that will be reimbursed.

Client participants will be reimbursed \$30 (in a choice of gift cards) for the baseline assessment. The initial client follow-up assessment one week after the Standard/PARS session is shorter so reimbursed at \$20. The 1, 3 and 6 month follow-up assessments are reimbursed \$30 each.

In addition, to minimize attrition, client participants will also be offered an additional incentive to be paid at the final 6-month assessment (or end of the 6-month assessment window if they do not complete it). The additional incentive (also in gift cards) will be \$20 for completing 2 of the 3 outcome assessments and \$30 for completing all outcome assessments.

Counselor participants will be reimbursed \$30 (in a choice of gift cards) for the baseline and follow-up assessments (i.e. every four months). Additionally, the counselor leading the study PARS group will receive an additional \$20 for completing the brief acceptability questionnaire after the first PARS group.

Stakeholder Participants [REDACTED]

4.5 Non-monetary compensation. Describe any non-monetary compensation you will provide. Example: extra credit for students; a toy for a child. If you will be offering class credit to students, you must provide (and describe) an alternate way for the students to earn the extra credit without participating in your research.

As reimbursement for attending and completing PARS Training, counselor participants will receive free National Association of Social Work CE Credits for the hours they participate in the PARS training.

4.6 Consent for recruiting and screening. Will you obtain consent for any of the recruiting and screening procedures? ([Section 8: Consent of Adults](#) asks about consent for the main study procedures).

“Consent” includes: consent from individuals for their own participation; parental permission; assent from children; consent from a legally authorized representative for adult individuals who are unable to provide consent.

Examples:

- For a study in which names and contact information will be obtained from a registry: the registry should have consent from the registry participants to release their names and contact information to researchers.
- For a study in which possible subjects are identified by screening records: there will be no consent process.
- For a study in which individuals respond to an announcement and call into a study phone line: the study team person talking to the individual may obtain non-written consent to ask eligibility questions over the phone.

	No
	Yes

→ If no, you must still answer [question 4.7](#) below.

→ If yes, describe the consent process.

There is no eligibility screening. See Section 2.1 and 4.1.

a. Documentation of consent. Will you obtain a written or verifiable electronic signature from the subject on a consent form to document consent for all of the **recruiting and screening procedures**?

No

→ If no, describe the information you will provide during the consent process and for which procedures.

Yes

→ If yes, upload the consent form to the **Consent Forms and Recruitment Materials** page of **Zipline**.

4.7 Data and specimens for recruiting and screening. For studies where you will obtain consent, describe any data and/or specimens (including any PHI) you will obtain for recruiting and screening (prior to obtaining consent) and whether you will retain it as part of the study data.

Obtain means to possess or record in any fashion (writing, electronic document, video, email, voice recording, etc.) for research purposes and to retain for any length of time.

Examples: names and contact information; the information gathered from records that were screened; results of screening questionnaires or screening blood tests; Protected Health Information (PHI) from screening medical records to identify possible subjects.

There is no eligibility screening. See Section 2.1 and 4.1.

